4.3. Subject Withdrawal or Termination

4.3.1. Reasons for Withdrawal or Termination

Subjects will be informed that they have the right to withdraw from the study at any time for any reason without prejudice to their medical care.

Subjects who withdraw consent prior to being randomized into the study will be recorded as having failed the eligibility criterion for study consent (signed ICF is no longer valid at the time of randomization).

The Investigator may consider terminating study drug and/or discontinuing subjects from the study for the following reasons:

• Continuing significant deterioration from baseline (≥7%) of BMD at spine or hip (after confirmation of the finding)

 Hypercalcemia, hypercalciuria, or excessive skin reactions as described in Section 4.7

- Severe hypersensitivity to abaloparatide or test materials
- Refusal of treatment
- Inability to complete study procedures
- Lost to follow-up
- SAEs (as described in Section 7.1.2)
- A complex of AEs or laboratory abnormalities which, in the judgment of the Investigator, justifies treatment cessation
- Serious intercurrent illness
- Noncompliance
- Protocol deviations
- Administrative reasons
- Incident vertebral or nonvertebral fragility fracture

4.3.2. Handling of Subject Withdrawals or Terminations

If a subject is withdrawn or discontinued from the study, the reason for withdrawal from the study is to be recorded in the source documents and on the eCRF. All subjects withdrawn prior to completing 12 months of study drug treatment should be encouraged to complete study procedures scheduled for the Month 12/End of Treatment (EOT) visit as soon as possible, and to return in 1 month for a Follow-up visit (EOS Visit). All AEs should be followed as described in Section 7. Subjects who discontinue prematurely or are withdrawn from the study will not be replaced. For early terminations that occur on or after the day of study drug initiation, every effort should be made to document the subject's outcome, regardless of cause. Whenever a subject is discontinued prematurely, the Sponsor's Medical Monitor must be notified.

4.4. Concomitant Medications

Subjects will be provided with calcium and vitamin D supplements to be administered daily from the Pretreatment Period until the end of the Treatment Period. The supplement dose will be determined by the Investigator and agreed by the Sponsor, according to subject's need to ensure that their daily intake of calcium and vitamin D is 1,200 mg/day and 800 IU/day, respectively. The doses and schedule of calcium and vitamin D supplements, which are part of the study drug protocol, should be adhered to and not be changed other than for medical necessity (Section 4.7). The supplements should be taken in the evening with or without food or as otherwise instructed by the Investigator.

For any required concomitant medication, such as statins or antihypertensives, the subject must be on a stable dose for 90 days prior to study entry and every effort should be made to maintain a stable dose during study participation.

The occasional use of over-the-counter medications at approved doses (eg, ibuprofen or acetaminophen) for headache or minor discomfort is allowed. Subjects should not take any other medications, including over-the-counter medications, herbal medications, or mega-doses of vitamins during the study, without prior approval of the Investigator.

If it becomes necessary for a subject to take any other medication during the study, the specific medication(s) and indication(s) must be discussed with the Investigator. All concomitant medications taken during the study must be recorded in the subject's medical record or source document and transcribed into the eCRF.

4.5. Prohibited Medications

Please refer to Section 4.2 for medication-related exclusion criteria.

Subjects should not take any other medications, including over-the-counter medications, herbal medications, or mega-doses of vitamins during the study without prior approval of the Investigator. The occasional use of over-the-counter medications (eg, ibuprofen or acetaminophen) for headache or minor discomfort will be allowed if discussed with the Investigator, recorded in the source documents, and in the subject's eCRF.

Use of corticosteroids for seasonal allergies or asthma is not prohibited. Use of low-dose corticosteroids (eg, ≤ 5 mg/day of prednisone or the relative equivalent dose of another corticosteroid) is also not exclusionary. Subjects who require chronic treatment with either an anticonvulsant (phenobarbital, phenytoin, carbamazepine, or primidone) or with heparin will be discontinued.

4.6. Premature Termination or Suspension of Study

This study may be temporarily suspended or prematurely terminated if there is sufficient reasonable cause. Written notification documenting the reason for study suspension or termination will be provided by the suspending or terminating party to the Principal Investigator and regulatory authorities. If the study is prematurely terminated or suspended, the Principal Investigator will promptly inform the Institutional Review Board (IRB) or Independent Ethics Committee (IEC) and will provide the reason(s) for the termination or suspension.

Circumstances that may warrant termination or suspension include, but are not limited to:

- Determination of unexpected, significant, or unacceptable risk to subjects
- Insufficient compliance with protocol requirements
- Data that are not sufficiently complete and/or evaluable
- Decision of Sponsor

The study may resume once concerns about safety, protocol compliance, or data quality are addressed and satisfy the sponsor, IRB/IEC, and/or Regulatory Agencies, if applicable.

4.7. Temporary Suspension of Treatment

The Investigator has the right to suspend treatment with study drug for up to 14 continuous days. Subjects can miss up to 28 cumulative days of dosing without withdrawal of the subject from the study. Reasons for temporary suspension of treatment may include a medical reason unrelated to an AE (eg, a planned procedure) or important social or administrative events. The reason for the suspension of treatment is to be documented and source verified during monitoring visits.

When treatment is restarted, the subject should resume treatment with the next scheduled dose and continue until the scheduled EOT.

Subjects who develop hypercalcemia or hypercalciuria during the study are to have treatment with calcium and vitamin D temporarily suspended as described below. The Investigator should contact the sponsor for any planned suspension of treatment or if suspension of treatment is contemplated.

4.7.1. Treatment Algorithm in Subjects who Develop Hypercalcemia

Hypercalcemia is defined as any serum calcium (albumin-corrected) that is ≥ 0.3 mg/dL (equivalent to ≥ 0.08 mmol/L) above the upper limit of normal (ULN). For this study, the normal range, ULN. and lower limit of normal (LLN) for serum calcium (albumin-corrected) are determined by the central laboratory.

For any predose serum calcium (albumin-corrected) value which is ≥ 0.3 to 1.0 mg/dL, corresponding to ≥ 0.08 to 0.25 mmol/L, above the ULN (inclusive), confirm hypercalcemia by drawing a new serum sample as soon as possible after the result is received (Figure 2).

- If the repeat serum calcium (albumin-corrected) is above the LLN up to < 0.3mg/dL (equivalent to < 0.08 mmol/L) above the ULN, the subject should continue study drug administration together with calcium and vitamin D supplementation.
 - If a subject's predose serum calcium is elevated on repeat testing, calcium and vitamin D supplementation should be withheld. The subject is to continue study drug administration during this interval.
 - If the subject's predose serum calcium remains elevated 1 to 2 weeks after calcium and vitamin D supplementation is withheld, dosing of study drug should be stopped.

Treatment can be restarted if other causes of hypercalcemia are excluded after consultation with the Sponsor. Treatment with study drug should not be suspended for greater than 14 days. If the subject continues in the study (with calcium and vitamin D supplements) and has a repeat episode of a predose serum calcium (albumin-corrected) value ≥ 0.3 to 1.0 mg/dL (corresponding to ≥ 0.08 to 0.25 mmol/L) above the ULN, repeat testing of the predose serum calcium (albumin-corrected).

• If the subject's serum calcium (albumin-corrected) value again returns to normal when not taking calcium and vitamin D supplements, the subject may continue in the study without calcium and vitamin D supplements.

• If the retest is still elevated, contact the Sponsor's medical monitor to assess whether the subject is to be discontinued from the study.

For any serum calcium (albumin-corrected) value >1.0 mg/dL above ULN:

- Discontinue calcium and vitamin D supplements and discontinue the study drug as soon as the result is received. Confirm hypercalcemia by drawing a new serum sample as soon as possible.
- If the result of the retest remains >1.0 mg/dL above ULN, perform a second retest after 3 days without calcium and vitamin D supplements and study drug.
 - If the second retest is normal, the subject may continue in the study and resume study drug, including the calcium and vitamin D supplements.
 - If the second retest is still elevated, contact the sponsor medical monitor to assess whether the subject is to be discontinued from the study.
- If the subject continues in the study and has a repeat episode of serum calcium >1.0 mg/dL above ULN, contact the Sponsor's medical monitor to assess whether the subject is to be discontinued from the study.

[figure not shown]

Figure 2: Treatment Algorithm in Subjects who Develop Hypercalcemia

^{*} For any predose serum calcium (albumin-corrected) >1.0 mg/dL (>0.25 mmol/L) above the upper limit of normal (ULN), immediately discontinue calcium, vitamin D, and study drug

^{**} ULN, lower limit of normal (LLN), and normal ranges are determined per the central laboratory

^{***} If applicable, also consider restarting/continuing vitamin D and calcium supplementation after consultation with the Sponsor

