#### **4.6.5.2. Hypercalcemia**

A hypercalcemic event (hypercalcemia) is defined as an elevated serum calcium (albumin-corrected) value  $\geq 0.3$  mg/dL (or  $\geq 0.08$  mmol/L) above the upper limit of the normal range (ULN).

Three cutoff levels of serum calcium (albumin-corrected) values will be defined:

- a.  $\geq$  ULN
- b.  $\geq$  ULN + 0.3 mg/dL (or  $\geq$  ULN + 0.08 mmol/L)
- c.  $\geq$  ULN + 1.0 mg/dL (or  $>$  ULN + 0.25 mmol/L)

The following summaries and analyses will be provided by treatment group for each of the cutoff levels above:

- Number (%) of subjects with at least one occurrence of a serum calcium (albumin-corrected) value above the cutoff level at each visit, timepoint, and overall (entire treatment period):
  - The corresponding 95% CI based on Wilson's Score method will be provided per treatment group.
  - For the number of subjects with at least one occurrence of a serum calcium (albumin-corrected) value above the cutoff level during the entire treatment period:
    - The treatment groups will be compared using the chi-square test.
    - The risk reduction between the treatment groups (calculated as Abaloparatide-sMTS – Abaloparatide-SC) will be provided together with the 95% CI based on Newcombe's method.
    - The relative risk reduction between the treatment groups (calculated as (Abaloparatide-sMTS – Abaloparatide-SC)/Abaloparatide-SC) will be provided together with the 95% CI based on Wald's method.
- Number of occurrences of a serum calcium (albumin-corrected) value above the cutoff level per subject during the entire treatment period
- The ratio of the total number of occurrences of a serum calcium (albumin-corrected) value above the cutoff level to the total number of serum calcium (albumin-corrected) blood samples per subject during the entire treatment period.

Mean ( $\pm$ SE) serum calcium (albumin-corrected) values will be plotted over study visit by treatment group. All serum calcium (albumin-corrected) results will be included in the plot, which will indicate the results at pre-dose and 4-hours post-dose at each visit, as applicable.

To evaluate the relationship between age and hypercalcemia, the number (%) of subjects with at least one occurrence of hypercalcemia at each visit and overall (entire treatment period) will be summarized by treatment group and age group (< 65, 65 - < 75, and  $\geq$  75 years).

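### The hypercalcemia cutoff differs by unit: 0.3 mg/dL is 0.075 mmol/L, not the printed 0.08, and SAP cutoff c pairs ≥ with > at the same value

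*Protocol*

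**What the plan says.** Protocol 4.7.1 defines hypercalcemia as an albumin-corrected serum calcium "≥ 0.3 mg/dL (equivalent to ≥ 0.08 mmol/L) above the upper limit of normal (ULN"). It uses the same pair of numbers twice more:

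- **Redraw trigger.** A predose value "≥ 0.3 to 1.0 mg/dL, corresponding to ≥ 0.08 to 0.25 mmol/L, above the ULN (inclusive") calls for a confirmatory sample.
- **Retest rule.** If the repeat is above the LLN "up to < 0.3mg/dL (equivalent to < 0.08 mmol/L) above the ULN", study drug and supplements both continue. If the repeat is elevated, "calcium and vitamin D supplementation should be withheld".

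The stop tier begins above +1.0 mg/dL. The footnote to Figure 2 gives it in both units as ">1.0 mg/dL (>0.25 mmol/L) above the upper limit of normal (ULN"), with a strict inequality in each.

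SAP 4.6.5.2 repeats the 0.3 / 0.08 definition and sets three cutoffs for the summaries. Cutoff b is at or above ULN + 0.3 mg/dL, or "ULN + 0.08 mmol/L". Cutoff c is at or above ULN + 1.0 mg/dL, or strictly above "ULN + 0.25 mmol/L". For subjects with at least one value over a cutoff during treatment, the SAP states: "The treatment groups will be compared using the chi-square test". It adds a risk difference and a relative risk reduction, each with a 95% CI.

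Neither document says which unit decides. SAP 4.6.5 converts laboratory values to SI units and normalizes them to a single set of reference ranges for the summaries.

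**The concern.** A threshold printed in two units should select the same samples in either. Here the upper end of the action band (1.0 and 0.25) converts at 0.25, while the lower end (0.3 and 0.08) implies 0.267. Both ends cannot be exact under one factor.

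Two uses depend on the threshold. At the site it decides the redraw and, on retest, whether supplements go on. In the SAP it decides which subjects count as hypercalcemic in a comparison between arms. If sites act on mg/dL and the summary is run in SI, a subject could be managed as hypercalcemic and not be counted as such.

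The two forms of cutoff c raise a similar question without any rounding: the number is the same, but the inequality is not.

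**Working it through.** **Inputs**

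| Pair | Place | mmol/L per mg/dL |
|---|---|---|
| 1.0 mg/dL, 0.25 mmol/L | Protocol 4.7.1 and Figure 2 footnote | 0.25 / 1.0 = 0.25 |
| 7.4 mg/dL, 1.85 mmol/L | SAP Appendix C, calcium low | 1.85 / 7.4 = 0.25 |
| 11.6 mg/dL, 2.9 mmol/L | SAP Appendix C, calcium high | 2.9 / 11.6 = 0.25 |
| 0.3 mg/dL, 0.08 mmol/L | Protocol 4.7.1, SAP 4.6.5.2 | 0.08 / 0.3 = 0.267 |

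The urine limit in Protocol 4.7.2 agrees with the first three rows. SAP Appendix C equates 2.1 mg/dL of creatinine with 185.64 µmol/L, a factor of 185.64 / 2.1 = 88.4. The urine pair of 0.4 mg/mg and 1.131 mmol/mmol then implies a calcium factor of 1.131 / 0.4 × 0.0884 = 0.250.

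**Reproducing the printed figure.** 0.3 × 0.25 = 0.075 mmol/L, which becomes 0.08 when rounded to two decimals. The figure is therefore explained by rounding.

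**Converting it back.** 0.08 / 0.25 = 0.32 mg/dL. The two forms disagree for an excess of 0.30 to <0.32 mg/dL (0.075 to <0.080 mmol/L). The band is 0.32 − 0.30 = 0.02 mg/dL wide, and the SI form sits 0.32 / 0.30 − 1 = 6.7% above the mg/dL form.

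**What happens to a retest at exactly +0.3 mg/dL**

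- In mg/dL, 0.3 is not below 0.3, so the value is elevated and supplements are withheld.
- In SI, 0.075 is below 0.08, so supplements continue.
- In both readings study drug continues at this step.

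**Which values can fall in the band.** Reporting precision is not stated, so these are assumptions about unnormalized results:

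- Results and ULN in steps of 0.01 mmol/L: none, since 0.07 / 0.25 = 0.28 and 0.08 / 0.25 = 0.32 mg/dL lie on either side.
- Steps of 0.1 mg/dL: one (+0.3).
- Steps of 0.01 mg/dL: two (+0.30 and +0.31).

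If results and ULN are reported to 0.1 mg/dL and each is converted and rounded to 0.01 mmol/L, the outcome at exactly +0.3 mg/dL depends on the ULN. Over the 11 possible ULNs from 10.0 to 11.0 mg/dL, the SI difference is 0.08 (met) for 6 and 0.07 (not met) for 5.

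**Normalized values.** Under SAP Appendix D the normalized value is L_s + β(φ − L_A), with β the ratio of the range widths. Since U_s = L_s + β(U_A − L_A), the normalized excess over the ULN is β times the raw excess. A raw excess of 0.08 mmol/L enters the band when 0.075 / 0.08 = 0.9375 ≤ β < 1. A raw excess of 0.07 enters it when 0.075 / 0.07 = 1.071 ≤ β < 0.08 / 0.07 = 1.143. So even where no raw value falls in the band, a normalized one can. The documents do not give β, so this shows possibility and not frequency.

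**Cutoff c.** 1.0 × 0.25 = 0.25 exactly, so both forms name the same point. A value at exactly +1.0 mg/dL counts in the mg/dL form and not in the SI form. The protocol places that value in the lower, inclusive band and starts the stop tier strictly above it.

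**The case against.** The best defence is that this is a rounded gloss on a rule written in mg/dL. In Protocol 4.7.1 each SI value is offered as a translation of the mg/dL value, and the body text of the stop tier is in mg/dL alone. SAP 4.6.5 says the central laboratory supplies conventional as well as SI units, so sites can apply mg/dL directly. On that reading the conflicting retest instructions arise only if someone lets the gloss override the rule. The consequence at that step is also small: supplements are withheld or not, and study drug goes on.

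Much of this stands as a limit on size. It makes mg/dL the likely deciding unit at sites, but no sentence says so, and the SAP summaries are run on SI-converted, normalized values. Rounding explains the 0.08 without making the two cutoffs agree. Nor is two-decimal SI a fixed convention here: the urine limit is printed as 1.131, and Appendix C prints 0.645, 1.613 and 2.997.

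It is also fair that the step counts describe raw readings, whereas albumin-corrected calcium is derived from two results and the summaries use normalized data. The counts therefore bear on site decisions, and no number of affected samples can be derived for the SAP tables.

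If SI results come in 0.01 steps, ≥ 0.075 and ≥ 0.08 select the same raw values, so at site level that correction might change nothing. On cutoff c, the intended inequality can be recovered from the protocol. If the SI form was meant to read ≥ as well, the cutoff would agree with itself but still differ from the protocol's stop tier.

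**Conclusion.** The point holds and is minor. On the documents' own factor, the SI form of the hypercalcemia cutoff should be 0.075 mmol/L. The printed 0.08 splits the definition, the redraw trigger, the retest rule and SAP cutoff b over an excess of 0.30 to <0.32 mg/dL, and that band contains the boundary value the ≥ is meant to include. Cutoff c is inconsistent only at exactly +1.0 mg/dL.

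The arithmetic needs no outside assumption. The practical effect does: it depends on reporting precision, on the normalization ratio and on which unit is used, none of which is stated. The number of affected samples is unknown and may be zero. The same rule applies to both arms, the outputs are safety summaries and a supplement decision, and the non-inferiority test on lumbar spine BMD is not affected.

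**What to change.** In Protocol 4.7.1 (definition, redraw trigger and retest rule) and SAP 4.6.5.2 (definition and cutoff b), replace 0.08 with 0.075 mmol/L, or state that mg/dL decides. In SAP cutoff c, write > ULN + 1.0 mg/dL (> ULN + 0.25 mmol/L), which matches the protocol's stop tier.

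The cost is a few characters in each document and no new data. If SI decides, moving from 0.08 to 0.075 mmol/L can only leave the cutoff b count unchanged or raise it, by values in the band. Using > in both forms of cutoff c can only leave that count unchanged or lower it, by values at exactly +1.0 mg/dL.

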4.7.2. Treatment Algorithm in Subjects who Develop Hypercalciuria

For a urine calcium:creatinine ratio > 0.4 mg/mg, corresponding to > 1.131 mmol/mmol, check the subject's predose serum calcium (albumin-corrected) and apply the algorithm outlined in Section 4.7.1 if calcium is elevated.

If the calcium:creatinine ratio is > 0.4 mg/mg and serum calcium is normal:

- Discontinue calcium and vitamin D supplements and recheck urine calcium:creatinine ratio after 7 days.
 - If the urine calcium:creatinine ratio continues to be > 0.4 mg/mg in the presence of normal serum calcium, the subject may continue in the study under medical supervision (and without receiving additional calcium and vitamin D supplements).
 - If the urine calcium:creatinine ratio returns to normal, the subject may restart calcium and vitamin D supplements and continue in the study.
- If the subject restarts the calcium and vitamin D supplements and hypercalciuria returns, calcium and vitamin D supplementation should be terminated. The subject may continue in the study under medical supervision.

Therefore, subjects with hypercalciuria will not be discontinued from the study in the absence of hypercalcemia except at the discretion of the Investigator

4.7.3. Treatment Algorithm for Subjects who develop Excessive Skin Irritation

Excessive skin irritation is defined as any severe assessment of irritation signs (Section 6.6.3.1) or symptoms (Section 6.6.3.2) on the 4-point scale or any lesions in the skin AESI as assessed by the Investigator (ie, eschar, ulcer ,or non-healing wound). Per the Investigator's discretion, the subject may be temporarily discontinued from study therapy. The Investigator should practice clinical judgment when determining when to resume study therapy (ie, resolution of excessive skin irritation). If sensitization is suspected, the Investigator should contact the Sponsor for further instructions and evaluation.

5. STUDY DRUG ADMINISTRATION AND MANAGEMENT

In this study, study drug administration is defined as abaloparatide-sMTS application or abaloparatide-SC injection.

5.1. Study Drugs

All study drugs are for investigational use only and are to be used only within the context of this study; administration of treatment is to be carried out as described in Section 5.4. Abaloparatide-sMTS patches and abaloparatide-SC cartridges for administration of study drugs will be supplied to the study site by the Sponsor.

5.1.1. Abaloparatide-sMTS

The abaloparatide-sMTS array patch is enclosed in a collar assembly for loading onto a spring-loaded applicator. The abaloparatide-sMTS dose will be 300 µg.

5.1.2. Abaloparatide-SC

Abaloparatide-SC injection is supplied as a sterile, colorless, clear solution in a glass cartridge which is pre-assembled into a disposable single-use pen. The pen is intended to deliver 30 once daily abaloparatide doses of 80 μ g in 40 μ L of solution. Each pen contains 3120 μ g/1.56 mL.

5.1.3. Calcium and Vitamin D Supplements

Calcium and vitamin D supplements will be sourced locally by the site and provided to the subjects at the expense of the Sponsor.

5.2. Medical Devices

The medical devices provided for use in this study include an abaloparatide prefilled pen for SC injection and an abaloparatide-sMTS for transdermal administration. The instructions for use of these medical devices are provided in the Pharmacy Manual and also included with the study drug.

